**8.3 Study procedures**

**Study period:**

All the assessments will be done at baseline, at day 10 and day 30.

Patients diary cards will be reviewed at each visit for symptoms and exacerbations

	Day 1	Day 3	Day 5	Day 10	Day 30
Initiation procedures					
Informed consent	X				
Medication history	X				
Vital signs	X				
Check for eligibility	X				
Sputum collection	X				
Blood sampling, including procalcitonin*	X				
Blood sampling CRP, eosinophils	x				
Serum for storage	X				
Sputum for storage	X				
Modified Anthonisen criteria	X	X	X	X	X
Clinical assessment for treatment failure		X	X	X	X
CAT	X			X	X
E-RS	X			X	X
EQ-5D-5L	X			X	X
iMCQ					X
Randomization	X				

Antibiotic consumption	X	X	X	X	X
Diary cards according to modified Anthonisen criteria**	X	X	X	X	X
Assessment of adverse effects	x	X	X	X	X

\* (PCT will only be reported for the randomised PCT group and not for the usual care group during the study period. The measurement will be performed in the usual care group but this will be blinded until the study ends.)

\*\* This symptom card will be evaluated on the given days by the patient

#### **8.4 Withdrawal of individual subjects**

After signing the informed consent, patients still are allowed to withdraw from the study. Every attempt will be made to collect the primary end-point. Withdrawal by the investigator will mainly be because of safety reasons and mostly constitute a treatment failure.

##### **8.4.1. Specific criteria for withdrawal (if applicable)**

N/A

#### **8.5 Replacement of individual subject after withdrawal**

No subjects will be replaced in the study as soon as the quatum is reached of randomised subjects.

#### **8.6 Follow-up of subjects withdrawn from treatment**

Patients who are withdrawn from the study will be invited for a follow up visit as detailed above, and otherwise it will be attempted to collect data on the primary end-points as long as this is within the agreement of the informed consent.

#### **8.7 Premature termination of the study**

N/A

### **9. SAFETY REPORTING**

#### **9.1 Section 10 WMO event**

In accordance to section 10, subsection 1, of the WMO, the investigator will inform the subjects and the reviewing accredited METC if anything occurs, on the basis of which it appears that the disadvantages of participation may be significantly greater than was foreseen in the research proposal. The study will be suspended pending further review by the accredited METC, except in so far as suspension would jeopardise the subjects' health. The investigator will take care that all subjects are kept informed.

#### **9.2 AEs, SAEs and SUSARs**

##### **9.2.1 Adverse events (AEs)**

In a clinical study, an AE is any untoward medical occurrence (i.e. any unfavourable and unintended sign [including abnormal laboratory findings], symptom or disease) in a subject or clinical investigation subject after providing written informed consent for participation in

---

the study. Therefore, an AE may or may not be temporally or causally associated with the use of a medicinal (investigational) product.

In the following differentiation between medical history and AEs, the term 'condition' may include abnormal e.g. physical examination findings, symptoms, diseases, laboratory, pulmonary function test (PFT).

All adverse events reported spontaneously by the subject or observed by the investigator or his staff will be recorded.

Common expected adverse events are:

- Diarrhoea
- Gastric complaints

### **9.2.2 Serious adverse events (SAEs)**

An SAE is classified as any untoward medical occurrence that, at any dose, meets any of the following criteria (a-f):

- a) Results in death;
- b) In life-threatening:  
The term 'life-threatening' in the definition refers to an event in which the subject was at risk of death at the time of the event, it does not refer to an event, which hypothetically might have caused death if it were more severe
- c) Requires inpatient hospitalization or prolongation of existing hospitalization  
A hospitalization or prolongation of hospitalization will not be regarded as an SAE if at least one of the following exception is met:
  - o The admission results in a hospital stay of less than 12 hours
  - o The admission is pre-planned (i.e., elective or scheduled surgery arranged prior to the start of the study);
  - o The admission is not associated with an AE (e.g., social hospitalization for purposes of respite care).However, it should be noted that invasive treatment during a hospitalization may fulfil the criterion of 'medically important' and as such may be reportable as an SAE dependent on clinical judgment. In addition, where local regulatory authorities specifically require a more stringent definition, the local regulation takes precedence.
- d) Results in persistent or significant disability / incapacity  
Disability means a substantial disruption of a person's ability to conduct normal life's functions
- e) Is a congenital anomaly / birth defect;
- f) Is another medically important serious advent as judged by the investigator

When a SAE is reported spontaneously by the subject or observed by the principal investigator or his staff it will be reported to the coordinating investigator in the ErasmusMC.

The coordinating investigator will report the SAEs through the web portal *ToetsingOnline* to the accredited METC that approved the protocol, within 15 days after the sponsor has first knowledge of the serious adverse reaction.

---

SAEs that result in death or are life threatening should be reported expedited. The expedited reporting will occur not later than 7 days after the responsible investigator has first knowledge of the adverse reaction. This is for a preliminary report with another 8 days for completion of the report.

### **9.2.3 Suspected unexpected serious adverse reactions (SUSARs)**

Adverse reactions are all untoward and unintended responses to an investigational product related to any dose administered.

Unexpected adverse reactions are SUSARs if the following three conditions are met:

1. the event must be serious (see chapter 9.2.2);
2. there must be a certain degree of probability that the event is a harmful and an undesirable reaction to the medicinal product under investigation, regardless of the administered dose;
3. the adverse reaction must be unexpected, that is to say, the nature and severity of the adverse reaction are not in agreement with the product information as recorded in:
  - a) Summary of Product Characteristics (SPC) for an authorised medicinal product;
  - b) Investigator's Brochure for an unauthorised medicinal product.

The coordinating investigator in the ErasmusMC will report expedited the following SUSARs through the web portal ToetsingOnline to the METC:

- SUSARs that have arisen in the clinical trial that was assessed by the METC;
- SUSARs that have arisen in other clinical trials of the same sponsor and with the same medicinal product, and that could have consequences for the safety of the subjects involved in the clinical trial that was assessed by the METC.

The remaining SUSARs are recorded in an overview list (line-listing) that will be submitted once every half year to the METC. This line-listing provides an overview of all SUSARs from the study medicine, accompanied by a brief report highlighting the main points of concern. The expedited reporting of SUSARs through the web portal ToetsingOnline is sufficient as notification to the competent authority.

The coordinating investigator will report expedited all SUSARs to the competent authorities in other Member States, according to the requirements of the Member States.

The expedited reporting will occur not later than 15 days after the sponsor has first knowledge of the adverse reactions. For fatal or life threatening cases the term will be maximal 7 days for a preliminary report with another 8 days for completion of the report.

### **9.3 Annual safety report**

In addition to the expedited reporting of SUSARs, the coordinating investigator will submit, once a year throughout the clinical trial, a safety report to the accredited METC, competent authority, and competent authorities of the concerned Member States.

This safety report consists of:

- a list of all suspected (unexpected or expected) serious adverse reactions, along with an aggregated summary table of all reported serious adverse reactions, ordered by organ system, per study;

- 
- a report concerning the safety of the subjects, consisting of a complete safety analysis and an evaluation of the balance between the efficacy and the harmfulness of the medicine under investigation.

#### **9.4 Follow-up of adverse events**

All AEs will be followed until they have abated, or until a stable situation has been reached. Depending on the event, follow up may require additional tests or medical procedures as indicated, and/or referral to the general physician or a medical specialist. SAEs need to be reported till end of study within the Netherlands, as defined in the protocol

#### **9.5 [Data Safety Monitoring Board (DSMB) / Safety Committee]**

An interim analysis will be performed at 50% of patient accrual, analysing the primary outcome and safety data. The safety data consists of observed adverse events and SAE. A DSMB will assess this interim analysis. The members of the DSMB will be dr. [name] (pulmonologist Franciscus Gasthuis & Vlietland), dr. [name] (medical microbiologist Erasmus Medical Center) and prof. dr. ir. [name] (Professor of Clinical Epidemiology of Cardiovascular Diseases Erasmus Medical Center). The advice(s) of the DSMB will only be sent to the principal investigator of the study. Should the principal investigator decide not to fully implement the advice of the DSMB, the principal investigator will send the advice to the reviewing Ethical Committee (in Dutch: METC), including a note to substantiate why (part of) the advice of the DSMB will not be followed.

Criteria on which the DSMB may decide to terminate the trial prematurely are:

1. Any serious adverse event related to the treatment under investigation has occurred.
2. A significant evidence of benefit

### **10. STATISTICAL ANALYSIS**

There will be two analysis populations for this study:

1. The Intention-to-Treat (ITT) population is defined as all randomised patients who took at least one dose of study drug.
2. The Per-Protocol (PP) population is defined as a subset of ITT population constituted by those patients who: a) met all inclusion/exclusion criteria, b) attained a sufficient compliance to the treatment received, treatment with prednisolone and/or antibiotics, when prescribed on admission for at least 5 days, and c) did not present serious deviations from the protocol.

The analysis of all the efficacy variables will be performed on both the ITT and the PP populations in order to assess the robustness of the findings from the ITT population. All the demographic and baseline patients' characteristics and safety outcomes will be analysed using the ITT population.

All efficacy variables will be analysed for ITT and the PPS, and the PP population will be considered the primary population for assessing efficacy.

---

### **10.1 Primary study parameter(s)**

The primary objective of this study is to show that at hospitalization for a severe exacerbation of COPD, PCT-guided treatment regarding antibiotic use is non-inferior to usual care consisting of prednisolone and or antibiotics, in terms of treatment failure at day 30 for patients hospitalized because of an acute exacerbation of COPD (AECOPD). Treatment failure is defined as disease-related mortality, need for endotracheal intubation or vasopressors, renal failure\*, lung abscess/empyema, development of pneumonia or rehospitalization within 30 days after inclusion.

\*renal failure is defined as Kidney Disease: Improving Global Outcomes (KDIGO) stage 3 – new renal replacement therapy, tripling of baseline creatinine, or serum creatinine  $\geq$  350  $\mu\text{mol/L}$ .

### **10.2 Secondary study parameter(s)**

Key secondary outcome:

- Treatment failure defined as an incomplete resolution of the clinical signs and symptoms associated with the AECOPD at day 30 after inclusion of the study (i.e not reaching the baseline condition prior to the AECOPD) scored using the modified Anthonisen criteria.

Other secondary outcomes:

- Change in Quality of Life on day 1, 10, and after 30 days using the COPD Assessment Test (CAT)
- Start of antibiotic therapy after an initial opposite decision (after 48 hours)
- Side effects (gastro-intestinal complaints, allergic reactions)
- Cumulative antibiotic consumption
- Cumulative prednisolone consumption
- Length of hospitalization
- Time to complete resolution of symptoms according to daily symptom diaries evaluating the modified Anthonisen criteria
- Re-exacerbation within 30 days
- PROM symptom score: EXACT – Respiratory symptoms scale (at admission, at day 10 and at day 30 after admission)
- ICU admission after 72 hours of admission
- Non-Invasive ventilation after 72 hours of admission

### **10.3 Other study parameters**

Demographics

Vital signs

Sputum for routine bacterial cultures

Serum sample for storage at -80 degrees Celsius

Sputum sample for storage at -80 degrees Celsius

Charlson comorbidity index

Cost effectiveness analysis, as detailed above in section 8.1.3

### **Statistical and analytical plans**

#### **Primary analysis**

The primary endpoint is defined as 30-day treatment failure. The per protocol (PP) population is the main analysis population. An analysis will be performed for the randomly

---

allocated antibiotic strategy (i.e. usual care versus antibiotics in patients with PCT >0.25 µg/L). The difference and corresponding 95% confidence interval (two-sided) in the incidence of the primary endpoint between the randomly allocated strategies (biomarker-guided drug use minus drug-in-all) will be determined. Non-inferiority will be concluded if the upper limit of the 95% confidence interval does not exceed the prespecified non-inferiority margin of 5%.

### **Secondary analyses**

The minimal clinically important difference (MCID) of the COPD Assessment Test (CAT) is considered to be a decrease of 2 to 3 points (after rehabilitation) and a decrease of 2 points according to Kon et al. who conducted 3 trials, in patients who underwent rehabilitation, patients who were admitted to the hospital because of an exacerbation and outpatient who were stable (24, 25). We will consider a decrease of 2 points as a minimal clinically important difference. The definition of symptomatic improvement of the E-RS is RS-total  $\geq$  -2.0 (scale range 0-40) (26). Adverse events will be compared by total number of adverse events, of serious adverse events, and separately for gastro-intestinal complaints. Differences in the incidence of these secondary endpoints between randomly allocated strategies will be analyzed by chi-square tests and logistic regression. Secondary endpoints consisting of continuous variables will be analyzed either using the unpaired t-test (for variables with normal distribution) or the Man-Whitney-U test (for variables with a skewed distribution). The distribution will be analyzed when the results are complete.

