6.4 Study Assessments

Visit	Baseline	Day 3	Day 5	Day 10	Day 30
Informed consent	x				
Medication history	x				
Vital signs	x				
Check for eligibility	x				
Sputum collection	x				
Blood sampling, including procalcitonin*	x				
Blood samples for CRP, eosinophils	x	x	x		
Serum for storage	x				
Sputum for storage	x				
Modified Anthonisen criteria	x	x	x	x	x
Clinical assessment for treatment failure		x	x	x	x
CAT	x			x	x
EXACT-RS	x			x	x
EQ-5D-5L + resp. bolt-on	x			x	x
iMCQ (adapted version)					x
Randomization	x				
Antibiotic consumption	x	x	x	x	x
Prednisolone consumption	x	x	x	x	x
Diary cards according to modified	x	x	x	x	x

Anthonisen criteria					
Assesment of adverse effects/events	x	x	x	x	x

* (PCT will only be reported for the randomised PCT group and not for the usual care group during the study period. The measurement will be performed in the usual care group but this will be blinded until the study ends.)

Analysis Time Windows

Visit (target day)	Lower bound (days)	Upper bound (days)
Baseline (0)	N/A	N/A
Day 3	N/A	N/A
Day 5	N/A	N/A
Day 10	9	11
Day 30	28	32

This section will go beyond the description of variables provided in the protocol in that it will list and describe all important study variables from a statistical perspective. The description of each variable should include:

- Modified Anthonisen criteria
 - Items are measured on with 3 optional answers where the first option = no deterioration, the second is slightly worse and the third option = much worse.
- EXACT respiratory symptoms questionnaire
 - Comprised of 11 questions about respiratory symptoms common for patients with COPD
 - Items are measured on a 0-3 or 0-4 ordered categorical scale for which a 0 = not at all, 1 = slightly or rarely or a little (depending on the question), 2 =moderately, 3 = severely or quite a bit, and 4 = extremely
 - The answer scales slightly differ depending on the question, for example breathlessness is scored on 0-3 ordered categorical scale for which a 0 = unaware of breathlessness, 1 = breathless during strenuous activity, 2= breathless during light activity, 3= breathless when washing or dressing, or present when resting
- COPD assessment test (CAT)
 - Comprised of 8 items to assess the impact of COPD on patients quality of life.
 - Items are measured on a 0-5 ordered categorical scale for which 0 = never experience this symptom to 5 = experience this symptom continuously

7 Sample Size

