10.2.2 Analyses of Secondary Endpoints

- Treatment failure defined as an incomplete resolution of the clinical signs and symptoms associated with the AECOPD at day 30 after inclusion of the study (i.e not reaching the baseline condition prior to the AECOPD) scored using the modified Anthonisen criteria.
 - Dichotomous variable (yes/no)
 - Description: Number and percentage
 - Test: logistic mixed-effects model
- Change in quality of life using the COPD assessment test
 - Measurements are continuous and paired (multiple (3) measurements in all patients (day 1, 10 and 30))
 - Description:
 - Normal distribution: mean score \pm SD
 - Skewed distribution: median (IQR)
 - Test:
 - mixed effects model with random effects for center and patient to account for the extra hierarchical level in the data. In case of violations of the normality assumptions, transformations of the dependent variable will be applied or the bootstrapping procedure will be used to obtain robust confidence intervals.
 - MCID = a decrease of 2 points after treatment is considered a minimal clinically important difference. When the difference in improvement of the CAT is < 2 points, then this will be considered a clinically non-significant difference[16,17].

- EXACT – Respiratory symptoms scale
 - Measurements are continuous and paired (multiple (3) measurements in all patients (day 1, 10 and 30))
 - Description:
 - Normal distribution: mean score \pm SD
 - Skewed distribution: median (IQR)
 - Test:
 - mixed effects model with random effects for center and patient to account for the extra hierarchical level in the data. In case of violations of the normality assumptions, transformations of the dependent variable will be applied or the bootstrapping will be used to obtain robust confidence intervals.
 - MCID: symptomatic improvement is defined by a decrease of the RS-total score of at least 2 points. When the difference in improvement of the EXACT is < 2 points, then this will be considered a clinically non-significant difference[18].

- Time to complete resolution of symptoms in days according to daily symptom diaries evaluating the modified Anthonisen criteria
 - Continuous variable, unpaired
 - Description:
 - Normal distribution: mean score \pm SD
 - Skewed distribution: median (IQR)
 - Test: mixed-effects model

- Decision to start antibiotic treatment after an initial opposite decision (after 48 hours)
 - Dichotomous variable (yes/no)
 - Description: Number and percentage

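### The protocol's sign for E-RS improvement contradicts the SAP, and the SAP's 2-point rule labels CAT and EXACT differences as clinically unimportant without looking at their confidence intervals

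*Protocol*

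**What the plan says.** **E-RS improvement.** Protocol, Secondary analyses: "The definition of symptomatic improvement of the E-RS is RS-total" ≥ −2.0, on a scale running from 0 to 40. The sentence does not say whether this is a change from baseline. SAP 10.2.2, on the same scale: "symptomatic improvement is defined by a decrease of the RS-total score of at least 2 points". The direction of scoring is in SAP 6.4: "Items are measured on a 0-3 or 0-4 ordered categorical scale for which a 0 = not at all", rising to 4 for extremely.

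**The 2-point rule.** For CAT, SAP 10.2.2 gives the MCID as a 2-point fall following treatment and then adds: "When the difference in improvement of the CAT is < 2 points, then this will be considered a clinically non-significant difference". For EXACT it has the parallel sentence: "When the difference in improvement of the EXACT is < 2 points, then this will be considered a clinically non-significant difference".

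**Planned analyses.** The SAP analyses both scales as repeated continuous measures, with a "mixed effects model with random effects for center and patient to account for the extra hierarchical level in the data". SAP Table 2 reports each as a mean or median change at days 10 and 30. It has no row for the proportion improved, and its effect column is blank for these two scales. The protocol has a general sentence for event-type secondary endpoints: "Differences in the incidence of these secondary endpoints between randomly allocated strategies will be analyzed by chi-square tests and logistic regression". It sends continuous secondary endpoints to a t-test or rank test.

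**The concern.** The protocol and the SAP define improvement on a named secondary endpoint in opposite directions. If someone built an E-RS responder variable from the protocol, the arm with less improvement would appear to have more improved patients.

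The 2-point rule matters more, because it sits in the SAP and will be followed. It moves a threshold framed as a fall after treatment onto the difference in improvement, which is naturally read as the difference between arms. It then attaches a conclusion to that difference with no condition on its precision. A true difference larger than 2 points can produce an estimate below 2, and an estimate below 2 can have an interval that runs well past 2. Quality of life is a stated secondary objective in both documents, so an unsupported statement of no clinical importance would bear on a planned conclusion.

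**Working it through.** **1. The two E-RS definitions side by side.** Among integer changes from −5 to +5:

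- Protocol sign (change ≥ −2): −2, −1, 0, +1, +2, +3, +4, +5 count as improved.
- SAP wording (change ≤ −2): −5, −4, −3, −2 count as improved.

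The sets share only −2. If the protocol figure is read as a raw score from 0 to 40, every patient meets it. Neither literal reading gives a usable definition of improvement.

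**2. What would follow if a responder comparison used the protocol sign.** The documents give no mean or SD for E-RS change, so these are assumptions: normal changes, mean −5.5 in one arm and −4.0 in the other, SD 4, 6 or 8. P(change ≤ −2) = Φ((−2 − mean)/SD); the literal rule gives one minus that.

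| SD | Improved, SAP wording | Difference | Improved, protocol sign | Difference |
|---|---|---|---|---|
| 4 | 81% vs 69% | +12 points | 19% vs 31% | −12 points |
| 6 | 72% vs 63% | +9 points | 28% vs 37% | −9 points |
| 8 | 67% vs 60% | +7 points | 33% vs 40% | −7 points |

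The direction reverses. This is conditional on an analysis that the SAP does not schedule.

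**3. The 2-point rule against the precision available.** Input from the documents: 315 evaluable patients per arm (protocol 10.4, SAP 8.5.5). Assumed: SD of the change score 6, 8 or 10, since neither document gives one; complete data; a simple two-group comparison. SE = SD × √(2/315) = SD × 0.0797. 95% CI = estimate ± 1.96 × SE. For an observed difference of 1.8 points:

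| SD | SE | Half-width | 95% CI for 1.8 | Largest estimate whose CI stays below 2 |
|---|---|---|---|---|
| 6 | 0.478 | 0.94 | 0.9 to 2.7 | 2 − 0.94 = 1.06 |
| 8 | 0.637 | 1.25 | 0.6 to 3.0 | 2 − 1.25 = 0.75 |
| 10 | 0.797 | 1.56 | 0.2 to 3.4 | 2 − 1.56 = 0.44 |

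In each row the interval excludes zero and includes values above 2, yet the SAP's label would be clinically non-significant. A smaller SD of 4 has a half-width of 0.62, and the interval for 1.8 still reaches 1.8 + 0.62 = 2.4.

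**4. How often a larger true difference would be dismissed.** P(estimate < 2) = Φ((2 − true difference)/SE). For a true difference of 2.5 points this is about 6% at SD 4, 15% at SD 6 and 22% at SD 8. For a true difference of exactly 2 points it is 50% at any SD.

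**The case against.** **On the sign.** It is most plausibly a notation slip. The protocol's preceding sentence describes the CAT threshold as a decrease, the SAP states the E-RS direction correctly in words, and the protocol's amendment section treats typing errors as non-substantial. A reader might infer that the trial's E-RS result will come out reversed. The documents do not support that. The SAP analyses E-RS as a continuous score and Table 2 has no responder row. The protocol's chi-square and logistic sentence follows directly on adverse events, and continuous endpoints have a sentence of their own. This part of the objection stands, and it limits the sign to a low-impact correction. The contradiction itself remains.

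**On the 2-point rule.** The SAP uses neither the term between-arm nor the term point estimate. It also foresees intervals: bootstrap intervals for these two scales in 10.2.2, and 95% CIs in the specification of Table 2. The sentence attaches a label and suppresses no estimate. At SD 8, an estimate up to about 0.75 has an interval wholly inside 2 points, so label and interval agree there. All of this is fair, but none of it ties the label to the interval: between about 0.75 and 2.0 points the label says more than the data can.

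**On direction.** A reader might also infer that the rule tilts the trial towards finding no harm from withholding antibiotics. The wording is symmetric. The stated objective is an improvement in quality of life under PCT guidance, and the rule equally blocks a claim of small benefit. Harm is also assessed through the primary composite, symptom resolution, non-invasive ventilation, adverse events and the DSMB.

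**Conclusion.** The concern holds in two parts of unequal weight. The protocol's E-RS definition has the wrong sign and contradicts the SAP. This needs correcting, but it would change a result only if the protocol definition were used for a responder comparison that the SAP does not plan.

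The 2-point sentences in SAP 10.2.2 are the more consequential part. With 315 per arm and an assumed SD of 6 to 10, a difference of 1.8 points would be called clinically non-significant while its 95% CI reaches 2.7 to 3.4. The size depends on assumed SDs and on reading the difference as one between arms. Adjustment for baseline could narrow the intervals, and losses from the per-protocol population would widen them. The error can go in either direction. Only the interpretation of secondary endpoints is affected; the primary non-inferiority test and the sample size are not.

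**What to change.** **Protocol, Secondary analyses.** Define E-RS symptomatic improvement as a change from baseline in RS-total of −2.0 or less, that is, a decrease of at least 2 points. This matches the SAP.

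**SAP 10.2.2.** Replace the two sentences on differences below 2 points with one rule for both scales: report the between-arm mean difference with its 95% CI at days 10 and 30; a difference of 2 points or more is ruled out only if the interval excludes it; where the interval contains both smaller and larger values, report the result as inconclusive on clinical relevance. Fill the blank effect cells for these rows in Table 2 accordingly. Because the 2-point figure is defined as a decrease after treatment, add a sentence saying why it is also used as a yardstick between arms.

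**Optional.** Report by arm the proportion of patients with a decrease of at least 2 points on each scale. The data are already collected at baseline, day 10 and day 30, and the cost-effectiveness analysis already needs this for CAT.

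**Cost.** One protocol sentence, two SAP sentences and, if wanted, two table rows. The downside is that some comparisons will be reported as inconclusive where the present text would give a firm label.
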